Participants at retention risk, based upon non-attendance at group meetings or inability to contact during 3-month phone calls, triggers a retention protocol. Depending upon the unique situation, the appropriate person (Group-Based interventionist, Self-Directed Coordinator, Outcomes Assessor) makes every effort to contact the participant for the purpose of understanding their perspective and any life situation that may have triggered the retention risk. For participants who are firm about decisions to terminate contact with the trial, every effort is made to keep the door open for a change in this decision at a later time. This is done by requesting the participant's permission to call at a later time to check it, the timing of such a call to be mutually agreed upon.

DATA FLOW

The trial has two main data flows. One is for recruitment and outcome assessment and the other is for intervention support. Data are collected using a variety of electronic systems including:

- **Snap Surveys.** Advanced software that allows for the customization of online data capture forms.
- **SharePoint.** A secure platform that houses the ELM website. SharePoint allows for sharing of data, documents, and publically accessible information.
- **CentrePoint.** A secure platform that transfers accelerometry to the Research Coordinating Unit (RCU).
- **Quantum Portal.** A secure platform that transfers participant lab results directly to the RCU.

Reports provided to investigators feature site-specific aggregated data on recruitment, outcomes, and intervention quality. Research Assistants and interventionists have access to the ELM website, but are limited to viewing only data pertinent to their site and job responsibilities.

Recruitment and Outcome Assessments

Outcomes collection begins at recruitment and continues in 3-month intervals over the 2-year follow-up period. The specific outcome variables collected can be found in the **Outcomes Assessment** section. The RCU provides recruitment reports and data tracking tables, via the ELM website, to help Research Assistants monitor recruitment and submission of outcome measures. **Figure 4** presents the flow of outcomes data.

[figure not shown]

Figure 4. Elm Trial Outcomes Data Flow

Intervention Assessments

The RCU provides delivery support for specific intervention components and reports on the quality of intervention delivery.

In the Group-Based arm, the RCU supports the intervention by delivering automatic text messages that are tailored to content presented in the prior week and sent on a pre-existing schedule. At selected group meetings, the RCU prepares personalized feedback reports for each participant. The RCU creates reports on intervention progress assessed as class attendance, weight loss compared to the goal of $\geq 5\%$ loss of baseline body weight, and step count compared to the goal of 10,000 steps on most days. The RCU also creates reports on 3 treatment fidelity measures:

- **Delivery.** Documentation of delivery of specific intervention components;
- **Receipt.** Participant self-reports of acquisition and understanding of specific group content;
- **Enactment.** Participant self-reports of daily vegetable intake, mindfulness habits, and old habit recognition.

These reports are uploaded weekly by the RCU to relevant receivers via the ELM website, including interventionists, participants, investigators, and Intervention Coordinating Unit supervisors.

In the Self-Directed arm, data collected by the Self-Directed Coordinator includes completed telephone calls and frequency of participant-initiated contacts. These data are sent to the RCU and displayed quarterly in aggregate form on the ELM website for review by the Self-Directed Coordinator, investigators, and the ICU supervisors.

Participants in both arms are able to view their own data and track their progress in step counts and weight change. The RCU also tracks frequency of daily log-ons to the ELM website by participants in both arms. **Figure 5** presents the flow of intervention data.

[figure not shown]

Figure 5. Intervention Data Flow

SAMPLE SIZE

The primary outcome of the trial is remission of MetS at 24 months. MetS remission (meeting criteria for <3 MetS components) is clinically relevant and the most common endpoint in MetS trials. Sample size was based upon the assumptions that the chi-square test will be used to compare proportions of participants who remit MetS at 24 months by trial arm, with an overall significance level of 0.05, and power of 85%. This requires a sample size of 117 participants per group, or a total sample size of 234.

Consideration must be given to the fact that the proposed trial employs a “partially clustered” design where clustering is present in only 1 of the 2 arms. The Group-Based Program is delivered to participants in groups, or clusters, of approximately 15 participants. Connection and interactivity within each of these “experimentally-induced” clusters is a key component. The intraclass correlation coefficient (ICC) measures the extent to which participant responses are influenced by the cluster to which they belong. Since this clustering feature is present in only one of the two arms, its effect is muted. Results from our previous studies are consistent with those of others [13-14] indicating that the ICC could reasonably range from 0.01 to 0.20. We conservatively assume an ICC of 0.15 and adjust the total sample size required to achieve 85% power to 286 per arm or a total sample size of 572. We adjust upward to 300 participants/arm, a total sample size of 600 participants, 120 participants at each of 5 clinical sites, and 8 intervention clusters per site.

ANALYSIS PLAN

Analyses will be performed using an intent-to-treat approach that includes all patients as randomized, regardless of treatment dose. All analyses will use two-sided tests conducted at $\alpha=0.05$. Basic summary statistics will be based upon cluster-adjusted chi-square tests and t-tests. If a distribution is non-normal, cluster-adjusted

Wilcoxon rank sum tests will be used. Supplemental analyses will include mixed effects regression models to account for cluster effects and control for important covariates. The impact of missing data will be evaluated using sensitivity analyses. If data are missing at random, multiple imputation will be employed. If data are not missing at random, an appropriate statistical model will be employed (e.g. a pattern mixture model with sensitivity analyses).

The primary hypothesis is achievement of a clinically significant MetS remission at 24 months in $\geq 40\%$ of the participants in the Group-Based program and $\leq 20\%$ of the participants in the Self-Directed program. Achieved rates will be observed, relative to these benchmarks, without statistical support. The primary statistical analysis will compare MetS remission at 24 months between the trial arms using a cluster-adjusted chi-square test. A secondary analysis will compare these rates using a mixed effects logistic regression model examining treatment over time (i.e., baseline through 24 months), a treatment*time interaction, and adjustments for age, gender, race/ethnicity, socioeconomic status, geographic site, BMI, number of co-morbidities, and number of MetS components. Random effects (e.g. random intercept, time, intervention cluster) will be included in the model only if they significantly improve model fit as determined by the likelihood ratio test.

Behavioral treatment targets will be compared by arm, without statistical support, as the proportion of participants achieving clinically significant goals (as presented in the hypothesized pathway in **Figure 3**), based upon the pre-determined benchmarks. Statistical support will be provided by a cluster-adjusted chi-square test. All other secondary and exploratory outcomes will be compared using the relevant cluster-adjusted t-test or chi square test. These comparisons will be conducted using data from post-intensive intervention, mid-maintenance, and end-of-treatment visits and trends over time will be examined. Supplementary analyses will use generalized linear mixed effects modeling, with a behavioral treatment target or weight as the outcome, treatment group as the primary predictor, random effects to account for time, site, and cluster, and selected covariates.

The health economic evaluation features the incremental cost effectiveness ratio (ICER) for the 2 trial arms, where the $ICER = (C_1 - C_0)/(E_1 - E_0)$, and C is intervention cost, E is effectiveness at remission of MetS, subscript 1 denotes the Group-Based arm, and subscript 0 denotes Self-Directed arm. The ratio yields the cost differential for MetS remission in the 2 trial arms. In addition, the ICER will be calculated for each Quality-Adjusted Life Year (QALY) gained. The analysis will be conducted from the commercial payer, public payer, and societal perspectives. Sensitivity analyses will be conducted to account for the potential influence of plausible changes in cost assumptions.

The projected benefits of disseminating the Group-Based Program will be modeled by combining the observed rate of MetS remission in the trial with published national estimates of cardiometabolic disease risk and added health care costs associated with MetS. Projections will focus on the number of potential cases of type 2 diabetes, coronary heart disease, and stroke averted, and potential healthcare savings, in the overall adult population, Medicare population (65+), adults on Medicaid, and privately insured adults.

Exploratory analyses examine the efficacy to treatments within important population subgroups. These comparisons will be presented by forest plots. Intervention fidelity within each treatment arm is monitored on an ongoing basis by the Intervention Coordinating Unit, with remediation delivered promptly when problems are identified. Observed fidelity data will be compared to the clinically significant goal of at least 80% adherence to key components for the overall trial, and stratified by geographic site.

TRIAL ORGANIZATION

Figure 6 presents the structure of this multi-site trial. Leadership is provided by an eight-member Steering Committee comprised of the Principal Investigators of all 5 sites, the Trial Chair, the Research Coordinating Unit Director, and the Intervention Coordinating Unit Director. Decision-making uses consensus as a primary strategy. Votes on key questions are carried by a majority. Intervention training and fidelity is overseen by the Intervention Coordinating Unit. Quality of Data transmittal is overseen by the Research Coordinating Unit. Scientific Committees guide all scientific aspects of the trial. An independent Data and Safety Monitoring Board approves the trial protocol, monitors data quality and safety, and monitors outcomes by trial arm. It makes recommendations to the investigators and the funder by providing independent reports simultaneously.

[figure not shown]

Figure 6. ELM trial organization

SAFETY MONITORING

This trial presents low risk to participants given the nature of the lifestyle interventions and the trial measurements collected. Participants are thoroughly screened prior to enrollment to ensure their ability to participate in lifestyle interventions. Nonetheless, several types of unanticipated problems and adverse events may occur and will be monitored. All potential events reported by a participant or staff member are documented using the *Adverse Events Form*. This form is submitted to the Research Coordinating Unit (RCU), which will then submit it to the Site Physician within a predetermined timeline. The Site Physician adjudicates the event following guidelines and reports back to the RCU. The RCU sends the completed adjudication form to the Chair of the Safety and Ethics Committee and Trial Chair, as described below. Summary reports are provided to the Rush IRB and the Data and Safety Monitoring Board. The Chair of the Safety and Ethics Committee can alert the Data Safety and Monitoring Board at any other time at his/her discretion.

Adverse Events

The following procedures occur dependent upon determination of the event.

- **Adverse Events** and **Serious Adverse Events** that are not Unanticipated Problems are submitted to the central IRB in the annual Continuing Review application. These events are officially reported to the Steering Committee at its monthly meeting and semi-annually to the DSMB.
- **Unanticipated Problems** are submitted to the central IRB within 1 week of the Safety & Ethics Committee's review. The Steering Committee is to be notified promptly, and in no case longer than one month from the Committee's review. The DSMB is to be notified quarterly.

A summary of this reporting process is presented in **Figure 7**.

Critical Alert Values

Immediate risk is posed, and actions are needed, for the following problems.

[figure not shown]
Blood Pressure Above 160/100. Should this event occur, the research assistant contacts the participant's provider or designee to obtain a recommendation for patient care, prior to the participant leaving. If the participant does not want their primary care physician to be contacted, then the research assistant contacts the Site Physician. If a provider cannot be reached within one hour or before the participant plans to leave, the safety protocol is as follows:

Blood Pressure between 160/100 and 180/110 and NO symptoms. Participant is told that their blood pressure is elevated and they need to see their doctor as soon as possible for repeat testing and evaluation.

Blood Pressure between 160/100 and 180/110 WITH symptoms, such as (but not limited to) chest pain, shortness of breath, blurred vision or headache. Participant is urged to go to the nearest Emergency Department.

Blood Pressure higher than 180/110. Participant is urged to go to the nearest Emergency Department.

Glucose < 40 or ≥500; Triglyceride > 1,000 All lab results are reviewed by the Site Physician prior to being sent to a participant. If the glucose alert occurs, the Site Physician contacts the participant or his/her provider within 24 hours. If the triglyceride alert occurs, the Site Physician notifies the participant by phone and advises him/her to contact his/her primary care provider.

*An *Unanticipated Problem* is an incident, experience, or outcome that meets all of the following criteria:

- The nature, severity, or frequency is unexpected
- It is related or possibly related to participation in the research.
- It suggests the research may place subjects at greater risk of harm than previously recognized.

Figure 7: Process of Unanticipated Problems and Adverse Event Reporting

REFERENCES

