Compare the Group-Based and Self-Directed arms on the behavioral risk factor targets of the treatment, and other secondary outcomes, at 6, 15, and 24 months.

Aim 2a: Compare the Group-Based and Self-Directed arms on the proportion of participants achieving clinically significant improvement in behavioral risk factor targets of treatment: (1) 2 cups of vegetables/day; (2) at least 150 minutes of moderate intensity physical activity/week; (3) either the maximum score, or an increase of ≥ 1 standard deviation of baseline distribution, on the 3-facet Mindfulness Questionnaire; and (4) a score of ≥ 4 on each of the four domains of the Self-Reported Habit Index (diet, physical activity, emotion control, and sensory awareness).

Aim 2b: Compare the Group-Based and Self-Directed arms on the secondary outcomes of: (1) $\geq 5\%$ loss of baseline weight; (2) kg of weight lost; (3) frequency of sugary beverage intake; (4) energy/vitality; (5) depressive symptoms; (6) social support for diet and exercise; (7) frequency of contacts with the health network; (8) perceived stress; (9) eating competence; (10) MetS components; (11) MetS severity; (12) Hemoglobin A1C; and (13) body mass index.

AIM 3.

Conduct a comprehensive health economic evaluation of the Group-Based and Self-Directed programs.

Aim 3a: Calculate the cost-effectiveness of the Group-Based relative to the Self-Directed programs. Cost-effectiveness is quantified using the Incremental Cost-Effectiveness Ratio and will reflect the cost of the programs in the two arms relative to their efficacy at promoting a sustained remission of the MetS.

Aim 3b: Model the projected clinical benefits and health care savings associated with dissemination of the Group-Based and Self-Directed programs.

Aim 3c: Compare the Group-Based and the Self-Directed programs on the number and dose of

medications, and health care utilization (primary care visits, specialty care visits, emergency room visits, hospital admissions) at 2 years.

EXPLORATORY AIMS

AIM 4.

Evaluate the consistency of impact and delivery across national sites.

Aim 4a: Explore the efficacy of the Group-Based and Self-Directed programs in subgroups defined by: geographic site, type of recruitment, age, gender, race/ethnicity, education, income, and number of MetS components.

Aim 4b: Explore the fidelity of delivery of the Group-Based and Self-Directed programs by geographic site.

TRIAL DESIGN

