Vital Status, Adverse Events, Co-Interventions	3, PII, 9, 12, MM, 18, 21, EoT	RA
Contact Info	B,3, PII, 9, 12, MM, 18, 21, EoT	RA
Five-Facet Mindfulness Questionnaire	B, PII, MM, EoT	RA
Eating Competence Questionnaire	B, PII, MM, EoT	RA
Demographics	B, PII, MM, EoT	RA
Labs (Lipid Panel, Glucose and A1c)	B, PII, MM, EoT	RA
Medical History	B, PII, MM, EoT	RA
NCI's Fruit and Vegetable Screener	B, PII, MM, EoT	RA
Food Log and Logistic Plan	B	RA
Perceived Stress Scale	B, PII, MM, EoT	RA
Depression: Patient Health Questionnaire (PHQ-8)	B, PII, MM, EoT	RA
Physical Measures (BP, HR, Waist, Weight, Height)	B, PII, MM, EoT	RA
Automatic Habits: Self-Report Habit Index	B, PII, MM, EoT	RA
Social Support for Diet and Exercise	B, PII, MM, EoT	RA
Sugar-Sweetened Beverage Intake	B, PII, MM, EoT	RA
Visit log	B, PII, MM, EoT	RA
Quality of Life: Short Form Health Survey (SF-36)	B, PII, MM, EoT	RA
Contacts with Health Network	B, PII, MM, EoT	RA
Prescription Medications	B, PII, MM, EoT	RA
MacArthur Ladder of Subjective Social Standing	B	PPT
USDA Food Security	B	RA
Treatment Credibility Questionnaire	B	PPT
Patient Preference for Each Treatment	B	RA
Program Satisfaction	EoT	PPT
Substance Use/Abuse - WHO ASSIST	B	RA

Montreal Cognitive Assessment	B	RA (if needed)
-------------------------------	---	----------------

Change of Status

The trial status of a participant refers to their level of participation in the trial. A *Participant Status Form* is completed whenever a status change occurs. All efforts are made to collect data on the primary outcome (MetS at 2 years), at the very least.

Lost-to-Follow-Up. A participant is considered “lost-to-follow-up” after missing two consecutive trial contacts without responding to messages, texts, or other forms of communication. Staff exhausts all avenues to locate the participant, including telephoning at least 10 times on different days, at varying times of day, contacting secondary contacts and the last medical provider on record, and checking online to identify new contact information. Failure of these attempts triggers a registered letter sent to the participant’s most recent address, to which non-response confirms the status as “lost-to-follow-up.”

Withdrawal from the Intervention. This status applies to a participant who no longer wants to participate in any intervention activities, but is willing to continue completing follow-up visits.

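### Three of the four Aim 2a improvement outcomes are fixed follow-up thresholds, and the planned test ignores baseline status, so participants already at target can count as improved

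*Combined protocol and SAP*

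**What the plan says.** Under Specific Aims, Aim 2a compares "the proportion of participants achieving clinically significant improvement in behavioral risk factor targets of treatment: (1) 2 cups of vegetables/day". The list goes on to "at least 150 minutes of moderate intensity physical activity/week", then the mindfulness target, then "a score of ≥ 4 on each of the four domains of the Self-Reported Habit Index". The vegetable, activity and habit targets are levels to be reached, with no condition on where the participant started. The mindfulness target is built differently: "either the maximum score, or an increase of ≥ 1 standard deviation of baseline distribution, on the 3-facet Mindfulness Questionnaire".

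The Analysis Plan describes the same outcomes as attainment of goals against preset benchmarks and refers to Figure 3 for them. On the test it says: "Statistical support will be provided by a cluster-adjusted chi-square test". Supplementary generalized linear mixed models are planned for the behavioural targets, but their covariates are not named.

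The Eligibility section requires readiness to change lifestyle and completion of a run-in. It contains no criterion that excludes a person who already eats, exercises or scores at the target level. Table 2 under Outcomes Assessment schedules the vegetable screener, accelerometry and "Automatic Habits: Self-Report Habit Index" at baseline and at all three follow-up visits.

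**The concern.** Improvement and attainment are different quantities, and the plan uses the two words for one outcome. A participant who ate two cups of vegetables a day before randomisation and still does so at 24 months has reached the goal but has not improved. Under Aim 2a as written, that person is a success. The Interventions section describes the participants as highly motivated, so some may well start at target.

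Aim 2a carries the behavioural step of the hypothesised pathway to remission. If its success rates mix new attainment with behaviour that was already in place, they cannot show how much behaviour changed. In some circumstances the comparison also loses sensitivity, and a real behavioural effect could be missed.

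**Working it through.** **The plan's own figure.** The documents give no rate, power or sample size for Aim 2a. The nearest figure is the 117 per group for the primary outcome. With 40% vs 20%, two-sided α = 0.05 and 85% power, n = [1.960√(2·0.3·0.7) + 1.036√(0.24 + 0.16)]²/0.20² = 92.7, so 93. Allowing for 20% loss, 93/0.80 = 116.25, so 117. The figure reproduces.

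**Inputs from the documents.**
- 300 per arm and ICC 0.15, in the Group-Based arm only (Sample Size).
- 20% loss at 24 months (Retention), so 240 analysed per arm.
- Groups of about 15, so about 12 analysed per group. Design effect 1 + 11 × 0.15 = 2.65.

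**Assumptions, not in the documents.**
- Share at target at baseline: b = 10%, 20% or 30%.
- New attainment among those below target: 40% Group-Based, 20% Self-Directed (borrowed from the remission hypothesis).
- Share of baseline achievers still at target at follow-up: either 90% in both arms, or 90% Group-Based and 70% Self-Directed.

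**Formulas.** With maintenance rate k and new attainment a in each arm:
- As written: p = b·k + (1 − b)·a; SE = √{[p₁(1 − p₁)·2.65 + p₂(1 − p₂)]/240}; power = Φ(difference/SE − 1.96).
- Adjusted for baseline status, all participants: the same, with p(1 − p) replaced by b·k(1 − k) + (1 − b)·a(1 − a).
- Share of Self-Directed successes already at target at baseline: b·k₂/p₂.

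**Worked case, b = 20%, equal maintenance.** p₁ = 0.18 + 0.32 = 0.50 and p₂ = 0.18 + 0.16 = 0.34, a difference of 16 points. SE = √[(0.25 × 2.65 + 0.2244)/240] = 0.0608, giving power 75%. Of the 34% of Self-Directed participants counted as improved, 18 points were at target from the start (18/34 = 53%). Adjusted variances are 0.018 + 0.192 = 0.210 and 0.018 + 0.128 = 0.146. SE = √[(0.210 × 2.65 + 0.146)/240] = 0.0541, giving power 84%.

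| Maintenance (Group-Based / Self-Directed) | At target at baseline | Success rates as written | Difference | Power as written | Power, baseline-adjusted | Self-Directed successes already at target |
|---|---|---|---|---|---|---|
| 90% / 90% | 10% | 45% vs 27% | 18 points | 86% | 90% | 33% |
| 90% / 90% | 20% | 50% vs 34% | 16 points | 75% | 84% | 53% |
| 90% / 90% | 30% | 55% vs 41% | 14 points | 63% | 76% | 66% |
| 90% / 70% | 10% | 45% vs 25% | 20 points | 92% | 94% | 28% |
| 90% / 70% | 20% | 50% vs 30% | 20 points | 91% | 95% | 47% |
| 90% / 70% | 30% | 55% vs 35% | 20 points | 91% | 96% | 60% |

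At 90% vs 80% maintenance, the as-written difference is 19/18/17 points and power 89/84/80%.

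**Restriction to those below target.** With n = 240(1 − b) per arm, group size 12(1 − b) and the design effect recalculated, the difference is 20 points and power 92/91/89%.

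**Sensitivity to the ICC.** At ICC 0.05 (design effect 1 + 11 × 0.05 = 1.55) with equal 90% maintenance, as-written power is about 96/89/78%.

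**The case against.** Attainment compared between randomised arms is a legitimate estimand. Baseline status is balanced in expectation, so the test is valid, and the Analysis Plan already speaks of goals. On this view the fault is mainly a label. That is right about validity: a reader might infer that the comparison between arms is biased, and nothing in the documents supports that.

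A reader might also infer that the contrast is necessarily diluted. It is not. The trial is about sustained behaviour, and only the Group-Based arm has monthly maintenance meetings, so less relapse there is a plausible treatment effect. At 90% vs 70% maintenance the whole 20-point difference survives, and with 30% at target at baseline the below-target analysis has slightly less power than the planned one (89% vs 91%). This part of the objection stands. It also tells against making the below-target subset the main analysis, which would discard maintenance effects and depart from the plan's commitment to analyse everyone as randomised.

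The numerical inputs are partly borrowed: 40% vs 20% is a remission hypothesis, and 0.15 is a deliberately conservative ICC. One set of baseline rates need not suit all three targets, least of all the joint four-domain habit criterion. Figure 3 is not shown and might qualify the goals. The supplementary models might include baseline, but the plan does not say so.

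None of this removes the mislabelling. Even at 90% vs 70% maintenance, 28/47/60% of Self-Directed participants counted as improved were already at target.

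**Conclusion.** The point holds for three of the four Aim 2a outcomes. It would be wrong to read it as a complaint that Aim 2a ignores baseline altogether, because the mindfulness target requires a rise of at least one baseline standard deviation or the maximum score.

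Whenever some participants start and remain at target, the proportion reported as improved is too high. That conclusion does not depend on the assumed attainment rates; only its size does. The loss of power is conditional. Under the stated assumptions, power falls to between 86% and 63% with equal maintenance, and hardly changes from about 92% when the Self-Directed arm relapses more. The documents do not show which applies.

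This concerns a secondary aim. The primary outcome is not affected, because every participant has the metabolic syndrome at entry. The change is still worth making: adjusting for baseline in all participants raises power in every scenario tabulated, from 86/75/63% to about 90/84/76% with equal maintenance. That adjusted calculation treats baseline status as yes/no and keeps the design effect at 2.65.

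**What to change.** 1. In Aim 2a and the Analysis Plan, rename the vegetable, activity and habit-index outcomes as the proportion at target. Leave the mindfulness definition as it is.
2. Compare these three outcomes in all randomised participants with a cluster-adjusted model that includes the baseline value of the same measure, and report the adjusted difference in proportions. Keep the habit criterion as a joint requirement on all four domains.
3. Add a supportive analysis of new attainment among participants below target at baseline, and use the word improvement only for that result.
4. Tabulate the proportion at target at baseline by arm, so that readers can judge how much room for improvement there was.

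No new data are needed, since the measures are already taken at baseline. The cost is analysis-plan wording and a little more analysis work. The supportive analysis has a smaller denominator. Because it selects people on a low baseline reading, regression to the mean will raise its rates in both arms, so it should be read as a contrast between arms and not as an absolute rate of change.

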Investigator preference for, and confidence in, a specific trial result can be an independent source of post-randomization bias triggering unintended interventions, treatment crossovers, co-intervention bias, and ascertainment bias. The potential for this bias in the ELM trial is minimized by targeting the mindset of the investigators. Their mindset has been shaped by presentations and discussions about objectivity as a hallmark of a scientific mindset, the need for discipline to keep preferences private, and the fallacy of expecting, in advance of a trial result, that one arm will be superior to the other. Trial arms have been renamed with neutral names: Group-Based (the treated group, previously the Eat Love Move (ELM) program); and Self-Directed (the enhanced care comparator). The blind is extended in trial operations to include: blinding to trial hypotheses but not to trial aims among all except the Principal Investigators; blinding to individual level treatment assignment among all but the interventionists; blinding of all but the senior biostatistician to the primary outcome of MetS; and blinding of interventionists to aggregated outcome data completion. Detection of risk of bias resulting from an absence of equipoise will be evaluated on an ongoing basis by assessing crossovers and co-interventions every 3 months, and assessing differential attrition monthly.

ELIGIBILITY

To be eligible for participation, 600 individuals must meet the inclusion criteria and not meet any of the exclusion criteria.

Inclusion Criteria

1. Men and women with MetS, defined by the Joint Interim Statement of the IDF, NHLBI, AHA,WHF, IAS, IASO [1]. To meet these MetS criteria the participant has ≥ 3 of the following 5 components:
 - a. Waist circumference of ≥ 102 cm for men and ≥ 88 cm for women;
 - b. Triglycerides ≥ 150 mg/dL or treatment for elevated triglycerides;
 - c. HDL cholesterol <40 mg/dL in men and <50 mg/dL in women, or treatment for low HDL;
 - d. Systolic blood pressure ≥ 130 mmHg; diastolic blood pressure ≥ 85 mm Hg; or treatment for hypertension;
 - e. Fasting plasma glucose 100-125 mg/dL (range inclusive) or on metformin
2. Age 18 years or older.

Exclusion Criteria

Safety:

3. Unable to walk 2 consecutive blocks without assistance; pain, tightness, or pressure in the chest during physical activity; dizziness or lightheadedness without clearance from their physician.
4. History of an eating disorder in the past 5 years.

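### Aim 3c tests medication dose at 2 years without defining a dose scale, a value for people off a drug, or any use of baseline prescriptions

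*Combined protocol and SAP*

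**What the plan says.** The wording of Aim 3c under Specific Aims is to "Compare the Group-Based and the Self-Directed programs on the number and dose of" the drugs that participants take. The same aim covers use of health services and sets the time point at 2 years. It names no drug classes, no unit and no rule for combining drugs.

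The health-economic paragraphs of the Analysis Plan deal with cost per remission, cost per QALY and projected savings. They do not return to medication dose, so the test comes from the general sentence: "All other secondary and exploratory outcomes will be compared using the relevant cluster-adjusted t-test or chi square test". For non-normal data, cluster-adjusted "Wilcoxon rank sum tests will be used". Tests are two-sided at 0.05, under an "intent-to-treat approach that includes all patients as randomized, regardless of treatment dose".

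Table 2 (Outcomes Assessment) lists "Prescription Medications" at baseline and at all three follow-up visits, without a coding rule. The inclusion criteria show that several drug classes will be present: treatment for triglycerides, for HDL and for hypertension, and the glucose criterion "Fasting plasma glucose 100-125 mg/dL (range inclusive) or on metformin".

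**The concern.** A t-test or rank test needs one number per participant, and a chi-square test needs one category. For dose of medications the plan defines neither, and the simple ways of supplying one behave very differently:

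- Adding raw units across drugs lets the drug with the largest unit size dominate the total.
- Averaging over current users removes those who stopped, who are the people of most interest.
- Using only the 2-year value leaves in all the between-person variation that was there before randomization.

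If the rule is chosen after data are in hand, that choice can decide the finding. At stake is the dose part of Aim 3c. It also bears on how remission is read, since four of the five MetS components in the inclusion criteria can be met by being on treatment.

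**Working it through.** The plan gives no effect size, standard deviation or power for Aim 3c, so there is no figure of its own to reproduce. From the documents: 300 per arm and 20% loss at 24 months, so 300 × (1 − 0.20) = 240 per arm, and two-sided 0.05. Every drug-use and change rate below is an assumption.

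**1. The off-drug rule can change the sign.** Assume that users of a drug take 10, 20 or 40 units in shares 0.40, 0.35 and 0.25.

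- Self-Directed mean: 0.40×10 + 0.35×20 + 0.25×40 = 21.0.
- In the Group-Based arm, suppose 50%, 25% and 5% stop at the low, middle and high dose, and nobody's dose rises. Still on the drug: 0.40×0.50 + 0.35×0.75 + 0.25×0.95 = 0.20 + 0.2625 + 0.2375 = 0.70, so 30% stop.
- Units still taken per baseline user: 0.20×10 + 0.2625×20 + 0.2375×40 = 16.75.
- Stopped counted as zero: 16.75 against 21.0, lower. Current users only: 16.75/0.70 = 23.9 against 21.0, higher.

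This was simulated with 2,000 trials of 240 per arm and no within-group correlation. Assumed use: 60% on this drug, and 25% on a second, unchanged drug at 500, 1000 or 2000 units.

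| Dose variable | Significantly lower in Group-Based (t / Wilcoxon) | Significantly higher (t / Wilcoxon) |
|---|---|---|
| First drug, current users only | 0% / 0% | 43% / 52% |
| Raw sum of both drugs, stopped = 0 | 3% / 41% | 2% / 0% |
| Both drugs on a common scale, stopped = 0 | 34% / 59% | 0% / 0% |
| First drug, stopped = 0 | 47% / 85% | 0% / 0% |

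If instead 30% stop at every dose level, the users-only comparison shows no difference (2–3% significant in each direction). Stopped = 0 on the first drug then detects the reduction in 84% (t) and 97% (Wilcoxon).

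**2. Separating classes and using baseline gives the power.** The second simulation also has 2,000 trials, 240 per arm and independent participants. Assumed use: 60% on a blood-pressure drug (10/20/40 units), 30% on a lipid drug (10–80) and 15% on metformin (500–2000). Only the blood-pressure drug changes, one level at a time.

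- Larger effect: 25% vs 10% of users reduce or stop; 5% vs 10% of participants start or increase.
- Smaller effect: 20% vs 10% reduce or stop; 5% start or increase in both arms.

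| Analysis | Larger effect | Smaller effect |
|---|---|---|
| t-test, summed raw dose at 2 years | 5% | 5% |
| t-test, 2-year blood-pressure dose, off-drug = 0 | 25% | 9% |
| t-test, change in that dose from baseline | 94% | 47% |
| Rank test, direction of change (−1/0/+1) | 96% | 51% |
| Number of drugs at 2 years | about 10% | 6% |
| Change in number of drugs | 59% | 17% |

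Re-runs that fill in unstated details differently move individual entries by a point or two. If every reducer stops outright, the second row rises to 47% for the larger effect. Within-group correlation is left out throughout, so all the powers are optimistic; the comparison between rows is what matters.

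**The case against.** The strongest reply is that the plan is silent here rather than wrong. It nowhere tells the analyst to add milligrams across drugs or to drop people who stopped, and including all participants as randomized fits coding a stopped drug as zero. Under that coding the simulation found no significant reversal beyond chance. This stands. A reader might infer that the stated test will reverse a true reduction. The documents do not support that, because reversal needs an analysis restricted to current users, which they do not prescribe.

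A reader might also infer that dose is unusable and should be abandoned. That fails too: change in blood-pressure dose has 94% power against 96% for the direction score. The gain comes from separating classes and using baseline.

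Three further replies stand in part:

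- The Analysis Plan adds that these comparisons use all three follow-up visits and that trends will be examined, and it plans supplemental mixed models with covariates. So single-visit testing is not all that is planned. But none of this text names medication dose or brings baseline prescriptions into the comparison.
- Aim 3c also compares the number of medications, which registers stopping. It does not register dose reduction, and without baseline its power in the assumed scenarios is only about 6–10%.
- The outcome is secondary, and all the magnitudes rest on assumed rates.

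**Conclusion.** The concern holds as a gap in definition with a practical cost. Medication dose is a named secondary outcome, but the plan gives no common scale, no off-drug value and no use of baseline in the test that applies to it. With off-drug as zero, the likely failure is a missed effect: about 25% power on 2-year blood-pressure dose against 94% on change from baseline for the larger assumed effect, and 9% against 47% for the smaller. Summing raw units brings the t-test to about 5%. A result in the wrong direction is a risk only if people who stopped are left out.

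These figures depend on assumed prevalences, dose levels and change rates that the documents do not give, and on ignoring clustering. The ordering of the methods is the firmer conclusion. The primary remission test and the cost-per-remission and cost-per-QALY analyses are not affected.

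**What to change.** Amend Aim 3c and the Analysis Plan before outcome data are examined by arm:

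1. Analyse medication separately for each MetS-related class (blood pressure, lipid, glucose), in all randomized participants.
2. Standardise dose within class by a stated conversion, and count documented non-use or stopping as zero. Treat a missing form as missing, under the plan's missing-data approach, and not as zero.
3. Compare end-of-treatment dose adjusted for baseline, or change from baseline, with a cluster-adjusted test.
4. Compare the number of medications adjusted for the baseline count.
5. As an alternative or sensitivity analysis, score each class as reduced or stopped, unchanged, or started or increased, coded without sight of the arm. This is simpler but ignores the size of the change.

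The cost is analysis wording and some coding of forms already collected at baseline and end of treatment; no visit is added. There would be three class-level comparisons, to be reported as secondary. This concerns only how an outcome is defined and makes no recommendation on prescribing.
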